### **3) Setting**

Subjects visiting the Prisma Health Wound Healing Center – Richland will be recruited to participate in this study.

### **4) Resources Available**

Documentation will be comprised of demographic information, medical histories, rates of infection/surgical intervention/amputation included in patient electronic medical records. Additionally, patient reported outcome measurements and compliance logs provided by the participants and PUSH Tool 3.0 assessments recorded by the provider will be analyzed.

A fellowship trained foot and ankle surgeon will lead the research team.

The research team will be comprised of practicing orthopaedic surgeons, wound center physicians and staff, research staff, orthopedic residents, and medical students.

### **5) Prior Approvals**

None

### **6) Study Design**

#### **a. Recruitment Methods**

Study participants will be recruited from the pool of patients visiting the Prisma Health Wound Healing Center – Richland. A research coordinator within the Prisma Health Orthopedics department will review weekly clinic schedules of participating providers at the Wound Healing Center to flag patients who may qualify for the study and are scheduled for an office visit. The provider who sees the patient will inform the patient of the research study during their office visit, screen to ensure eligibility criteria are met, and, if appropriate, consent the patient to participate in the study.

## **b. Inclusion and Exclusion Criteria**

### Inclusion Criteria:

- $\geq 18$  years of age at the time of informed consent
- Toe blood pressure (TBP)  $>40$  mmHg
- Hemoglobin A1c  $<10\%$  (measured within the previous 6 months). If a patient has not had an A1c within 6 months of study enrollment, one will be performed at the time of enrollment to confirm study eligibility.
- Diagnosis of diabetes mellitus
- Presence of at least one new chronic, non-healing (present for  $\geq 4$  weeks), lower extremity wound (Wagner stage 1-2)
- Documented lipid panel within 3 months of study enrollment. If a patient has not had a lipid panel within 3 months of study enrollment, one will be performed at the time of enrollment to confirm study eligibility.
- Documented CMP within 3 months of study enrollment. If a patient has not had a CMP within 3 months of study enrollment, one will be performed at the time of enrollment to confirm study eligibility.
- Documented INR/PT within 3 months of study enrollment. If a patient has not had an INR/PT within 3 months of study enrollment, one will be performed at the time of enrollment to confirm study eligibility.
- Documented normal ECG within 3 months of study enrollment. If a patient has not had an ECG within 3 months of study enrollment, one will be performed at the time of enrollment to confirm study eligibility.
- Receiving standard of care defined as sharps debridement, appropriate dressing, and offloading.

### Exclusion Criteria:

- Allergy to fish
- History of hypersensitivity reactions to LOVAZA or any of its components
- Current smoker
- Currently taking any OTC supplements containing Omega-3 fatty acids, L-Arginine, or Vitamin C, or antibiotics
- Presence of at least one of the following diseases or conditions:
  - End stage renal disease as defined by patients who have been diagnosed with Stage 4 kidney disease and are not on hemodialysis or who are on hemodialysis with a GFR consistently  $< 15$  L/min and BUN  $> 60$ .
  - Hepatic impairment as defined by patients with a Child-Turcotte-Pugh score  $\geq 2$  based on a CMP/INR/PT performed within 3 months of study enrollment.
  - Paroxysmal or persistent atrial fibrillation
  - Untreated deep bone infection (osteomyelitis)
  - Currently pregnant or breastfeeding
- Women of child-bearing potential
- Prisoners and other institutionalized individuals
- Any patients who have a legal representative to make medical decisions on their behalf or any individuals who are otherwise deemed as medically incompetent.

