  - a. If randomized to the control group (SOC only), patients will receive standard of care defined as sharps debridement, appropriate dressing, and offloading. If randomized to the treatment group (SOC + Immunonutrition), subjects will receive standard of care defined as sharps debridement, appropriate dressing, and offloading in addition to a 6-week supply of Omega-3 fatty acids (soft gel form, 2 pills per day, total of 1.68 grams) and L-Arginine/Vitamin C (powder form, to be mixed with 8 oz liquid, 1 scoop once daily, total of 4.5 grams L-arginine and 500 mg vitamin C). Subjects will also be provided a compliance log with detailed instructions for taking and tracking supplements.
5. Patients will be scheduled for biweekly wound checks with their provider (weeks 2, 4, 6). Wound characteristics will be documented at each follow up visit using the PUSH Tool 3.0, images of the wound will be obtained, and an interval history and physical exam will be documented. The provider will verify and document concomitant medications in the patient's chart. The provider will visualize and evaluate any additional wounds that are present (new or present at time of enrollment) and record characteristics in the patient's chart. Patients will complete a questionnaire detailing their pain level (VAS), symptoms experienced during the treatment phase, and any unscheduled visits to emergency departments/urgent care centers. This will be completed via a paper survey in clinic during their office visit (Appendix 4). On weeks where an office visit is not scheduled (weeks 1, 3, 5), a research coordinator will call the patient and collect survey responses (Appendix 3).
6. At the final office visit (week 6), plantar pressure profiles will be recorded via the Tekscan Pressure Mat, and clinical plantar weight-bearing images will be captured. Patients randomized to receive the oral immunonutrition supplementation will complete an additional survey detailing their satisfaction with the treatment plan and any additional thoughts they would like to share (Appendix 5) and return the completed compliance log

(Appendix 6). Patients in the treatment arm will have CMP and lipid panel labs drawn at this timepoint or within 3 months of study completion.

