#### Omega-3 fatty acids (LOVAZA), 1.68 grams/day:

The FDA states that  $\leq 3.0$  grams/day of EPA + DHA is safe for humans. The daily supplementation provided to patients per this protocol is 1.68 grams/day (0.93 grams/day EPA + 0.75 grams/day DHA), well below the tolerable threshold.

Possible side effects associated with omega-3 fatty acid supplementation (LOVAZA) include eructation, dyspepsia, taste perversion, constipation, gastrointestinal disorder, vomiting, increased ALT, increased AST, pruritus, rash, hemorrhagic diathesis, urticaria.

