#### **If the subject is enrolled in the treatment arm (received oral immunonutrition supplementation), proceed with questions 3 and 4. If not, skip to question 5:**

- 3) **Verification of supplementation:** "Did you receive supplementation and instructions on how it should be taken?"
  1. **If No:** "May I ask why not?"
  2. **If Yes:** *proceed to number 3*
- 4) **Medication compliance:** "Have you been able to take the supplementation daily as instructed?"
  1. **If No:** "May I ask why not?"
  2. **If Yes:** *proceed to number 3*
- 5) **Experienced symptoms:**
  1. "Have you experienced any of the following symptoms during your participation in the study. Please answer yes or no to each"
    - Abdominal pain, heartburn, nausea, vomiting, diarrhea, headache, insomnia, rash, indigestion, palpitations, numbness, bitter taste, low blood pressure, burping, taste perversion, constipation, gastrointestinal disorder, itchy skin, easy bleeding or bruising, red itchy welts
    - "Have you experienced any other symptoms"
      - If yes:** "can you please explain?"
      - If no:** *proceed to number 5*
- 6) **Emergency Department / Urgent Care Visits:** "Since beginning this study, have you had any unscheduled office visits, or have you been to any emergency departments or urgent care centers related to your foot ulcer?"
  1. **If Yes:** "Can you please explain?"
  2. **If No:** *proceed to number 6*

"Thank you for your time (*Patient name*), I hope you have a good day."

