## Appendix 6: Supplement Compliance Log

Effects of Supplemental Immunonutrition on Healing of Chronic Non-healing Lower Extremity Ulcers in Diabetic Patients Compliance Log							
Date Consented:							
Date Supplement Received: <small>(Record the date that you were provided your supplements from Hawthorne Pharmacy)</small>							
Supplement Instructions:  Lovaza capsules Take 2 gel capsules by mouth daily.  Arginine/Vitamin C Powder Mix one scoop of powder into 8 oz water, juice, or gatorade and drink once daily.							
Instructions for completing compliance log: Week 1, Day 1 should be recorded as the first day AFTER you receive your supplements from Hawthorne Pharmacy. Indicate with a check mark when you take each supplement (2 Lovaza capsules and 1 Arginine/Vitamin C scoop) daily. Days should be consecutive. Do not skip days between doses. You will take these supplements every day for 6 weeks. Please be accurate in your reporting - ex - if you only take 1 Lovaza capsule on day 3, only record one check mark for this supplement.							
Week 1							
Day 1 Date:	Day 2 Date:	Day 3 Date:	Day 4 Date:	Day 5 Date:	Day 6 Date:	Day 7 Date:	
Lovaza capsule (2 capsules/day): _____	Lovaza capsule (2 capsules/day): _____	Lovaza capsule (2 capsules/day): _____	Lovaza capsule (2 capsules/day): _____	Lovaza capsule (2 capsules/day): _____	Lovaza capsule (2 capsules/day): _____	Lovaza capsule (2 capsules/day): _____	
Arginine/Vitamin C Powder (1 scoop/day): _____	Arginine/Vitamin C Powder (1 scoop/day): _____	Arginine/Vitamin C Powder (1 scoop/day): _____	Arginine/Vitamin C Powder (1 scoop/day): _____	Arginine/Vitamin C Powder (1 scoop/day): _____	Arginine/Vitamin C Powder (1 scoop/day): _____	Arginine/Vitamin C Powder (1 scoop/day): _____	
Week 2							
Day 1 Date:	Day 2 Date:	Day 3 Date:	Day 4 Date:	Day 5 Date:	Day 6 Date:	Day 7 Date:	
Lovaza capsule (2 capsules/day): _____	Lovaza capsule (2 capsules/day): _____	Lovaza capsule (2 capsules/day): _____	Lovaza capsule (2 capsules/day): _____	Lovaza capsule (2 capsules/day): _____	Lovaza capsule (2 capsules/day): _____	Lovaza capsule (2 capsules/day): _____	
Arginine/Vitamin C Powder (1 scoop/day): _____	Arginine/Vitamin C Powder (1 scoop/day): _____	Arginine/Vitamin C Powder (1 scoop/day): _____	Arginine/Vitamin C Powder (1 scoop/day): _____	Arginine/Vitamin C Powder (1 scoop/day): _____	Arginine/Vitamin C Powder (1 scoop/day): _____	Arginine/Vitamin C Powder (1 scoop/day): _____	
Week 3							

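### The supplement exclusion covers only over-the-counter products in current use, so omega-3 from any other source does not exclude a patient, and neither survey asks about own-source use during the 6 weeks

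*Combined protocol and SAP*

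**What the plan says.** **Eligibility.** Section 6.b excludes patients "Currently taking any OTC supplements containing Omega-3 fatty acids, L-Arginine, or Vitamin C, or antibiotics". The only other criterion that names the study's omega-3 product is "History of hypersensitivity reactions to LOVAZA or any of its components", which concerns past reactions and not current use.

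**Supply.** Section 6.f gives the omega-3 component as "soft gel form, 2 pills per day, total of 1.68 grams". Section 7 gives its content as "1.68 grams/day (0.93 grams/day EPA + 0.75 grams/day DHA), well below the tolerable threshold", set against a cited statement that up to 3.0 "grams/day of EPA + DHA is safe for humans". The subject of the margin sentence is explicit: "The daily supplementation provided to patients per this protocol is 1.68 grams/day". The compliance log (Appendix 6) asks the patient: "Record the date that you were provided your supplements from Hawthorne Pharmacy".

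**Monitoring of other use.** Sections 6.f and 6.i have concomitant medications verified and recorded at visit 0 and at weeks 2, 4 and 6, in both arms. In the phone survey (Appendix 4) the supplement questions are restricted: "If the subject is enrolled in the treatment arm (received oral immunonutrition supplementation), proceed with questions 3 and 4. If not, skip to question 5". Question 2 of the clinic survey (Appendix 3) goes to everyone, but it asks whether the patient received the supplements, and a patient who answers no skips ahead to the symptom list.

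**Use in analysis.** The covariates in Section 6.h are initial wound size, diabetes etiology, sex, race and age. Intake of these nutrients from outside the study does not enter any model.

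**The concern.** The evident purpose of the exclusion is to keep background users of the three nutrients out, so that the arms differ by the intervention. The over-the-counter limit leaves part of that purpose unmet. The study's omega-3 is a named product dispensed through a pharmacy, and a patient already taking it from a source that is not over the counter meets every listed criterion.

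The criterion also looks only at the moment of screening. The available text gives no rule on recent use and none on starting these products before week 6. No placebo is described, so controls know they are not receiving nutrients that Section 1 itself calls widely available.

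Two things are at stake. Use among controls moves them towards the treated condition and shrinks the contrast that a pilot with 15 per arm is meant to describe. In the treatment arm, total omega-3 intake can be higher than the study supply on which Section 7 bases its margin.

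**Working it through.** **1. The plan's own omega-3 figure (Section 7).** 0.93 + 0.75 = 1.68 g/day, which reproduces. With 2 capsules a day (Section 6.f), each supplies 1.68 / 2 = 0.84 g.

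**2. Headroom for a treated patient.** 3.0 − 1.68 = 1.32 g/day. Total intake = 1.68 + 0.84 × (own capsules of the same product per day):

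| Own capsules/day | Treated patient, total g/day | Above 3.0? |
|---|---|---|
| 0 | 1.68 | no |
| 1 | 2.52 | no |
| 2 | 3.36 | yes |

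A control who starts the study amount reaches 1.68 g/day, which is below the cited figure. Specific Aim 1 gives the omega-3 amount as 2 g. If all of that were EPA + DHA, headroom would be 3.0 − 2.0 = 1.0 g/day. One extra capsule at 0.84 g would still fit and two (1.68 g) would not, so the capsule count at which the figure is passed does not change.

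**3. Dilution of the contrast.** Let f be the share of controls using the nutrients, k the fraction of the full effect each user obtains (0 to 1), and p_t and p_c the uncontaminated outcome rates.

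Observed control rate = p_c + f·k·(p_t − p_c), so observed difference = (1 − f·k)(p_t − p_c).

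| Users among 15 controls | f | Shrinkage, k = 1 (upper bound) | Shrinkage, k = 1/3 (illustration) |
|---|---|---|---|
| 1 | 1/15 | 6.7% | 2.2% |
| 2 | 2/15 | 13.3% | 4.4% |
| 3 | 3/15 | 20.0% | 6.7% |

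The numbers of users and the values of k are assumptions; the documents give neither. The value k = 1/3 only illustrates a user who takes one of three nutrients.

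**4. What the upper end would do to power.** The plan states no closure rates, significance level or power. Assuming a two-sided 5% level, 15 per arm, 20% closure in controls, and f = 20% with k = 1:

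| Assumed closure, control vs treated | Normal-approximation power, f = 0 → 20% | Fisher exact power, f = 0 → 20% |
|---|---|---|
| 20% vs 40% | 22% → 15% | 11% → 7% |
| 20% vs 50% | 40% → 27% | 25% → 14% |
| 20% vs 70% | 82% → 60% | 68% → 43% |

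**5. What the surveys can detect.** The phone survey skips controls on supplements. The clinic survey question asks about receipt, which identifies the arm but does not ask about products obtained elsewhere. The concomitant-medication record is therefore the only route by which own-source use by controls is likely to be seen, and the available text attaches no rule or analysis to it.

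**The case against.** The strongest reply is that use is largely visible already. Concomitant medications are checked in both arms at every office visit, clinic survey question 2 is put to controls, and the withdrawal grounds in Section 6.k are not a closed list. This stands in part: use can be detected and analysed. But the record does not act on eligibility, the survey question is not worded for own-source use, and no analysis is planned.

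Several stronger readings are tempting and are not supported.

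- A reader might infer that the Section 7 margin statement is false. It is not. Its subject is the supply under this protocol, and for that it stays true. It is silent on other sources.
- A reader might infer that the protocol's intake limit is breached. The 3.0 g/day figure is a cited safety statement, not a limit that the protocol sets or monitors. Passing it takes more than 1.32 g/day of other EPA + DHA in a treated patient. Controls who take up the study amount do not reach it.
- A reader might infer that contamination would hide the signal. No effect size or contamination rate is given, and power for moderate effects is low at 15 per arm even with no contamination.
- A reader might take it as given that LOVAZA is available only on prescription. The documents do not say so. Pharmacy supply does not settle it, because the compliance log refers to the same pharmacy for all the supplements, including the powder.

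Finally, an instruction to avoid own-source products may sit in the consent pages, which could not be checked.

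**Conclusion.** The point holds as a gap in wording and data capture. The exclusion does not reach omega-3, L-arginine or vitamin C from sources that are not over the counter, and the available text does not address recent use or starting these products on study. That conclusion rests on the text alone.

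Its size is conditional. One to three users among 15 controls would shrink the contrast by at most 7% to 20%, a ceiling that assumes full effect in each user. The excess over 3.0 g/day arises only for a treated patient who already takes two or more capsules a day of the same product. How many eligible patients take such products cannot be learned from the documents. The gap is worth closing because doing so is cheap and the trial is small, not because the design is shown to fail.

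**What to change.** 1. **Section 6.b:** remove the over-the-counter limit, so that the exclusion covers current use of omega-3, L-arginine or vitamin C supplements from any source.
2. **Clinic and phone surveys (Appendices 3 and 4):** add one item for every patient, controls included, asking whether any such product was taken from outside the study since the last contact, and which one.
3. **Section 6.h:** pre-specify that own-source users are counted by arm, from the new item and the concomitant-medication record, and that the main comparison is repeated with them set aside. The comparison by assigned arm should remain the main result, because use that starts after randomisation is not protected by it. With 1 to 3 users, 14 to 12 controls would remain, so this analysis would be descriptive.
4. **Sections 6.b, 6.f and 7:** the sponsor should reconcile these on recent and on-study use, and state whether the omega-3 margin refers to study supply or total intake. The 2 g in Specific Aim 1 and the 1.68 g elsewhere should be reconciled at the same time.

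No washout length and no instruction about prescribed medication is proposed; Section 6.f refers to five half-lives but gives no half-life figure. The cost is protocol wording, one survey item and one analysis, with a few patients on prescribed omega-3 becoming ineligible.

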**c. Local Number of Subjects**

This is a pilot study which aims to enroll 30 patients locally, 15 per arm.

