### **k. Withdrawal of Subjects**

Subjects may withdraw from the study at any time. All data recorded to that point may be kept and used for data analysis.

The provider has the authority to remove any subject from the study at his/her discretion, at which time the provider will inform the subject of withdraw. Circumstances for withdraw include, but are not limited to:

- a. Failure to meet inclusion/exclusion criteria (labs, A1c, ECG parameters)
- b. Lack of compliance with supplementation
- b. Rapid progression of wound(s) which is expected to result in surgery during the 6-week study period
- c. Severe adverse effects which are possibly related to supplementation

All data recorded to the point of withdraw may be kept and used for data analysis.

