### **9) Safety Monitoring Plan**

#### Laboratory Monitoring:

Periodic laboratory and ECG monitoring will be performed to assess safety of the oral supplement as detailed below:

**Lipid panel monitoring:** patients are eligible for study participation if they have had a lipid panel performed within 3 months of study enrollment. An additional lipid panel will be performed at study conclusion (6-week timepoint or within 3 months of study completion) for patients enrolled in the treatment arm.

**Blood glucose monitoring:** blood glucose is routinely monitored in diabetic patients at our institution. This data will be reviewed in the patients' charts as they become available, and the investigators will be alerted to any abnormalities.

**Serum chemistry parameters and hepatic enzymes:** patients are eligible for study participation if they have had a CMP performed within 3 months of study enrollment. An additional CMP will be performed at study conclusion (6-week timepoint or within 3 months of study completion) for patients enrolled in the treatment arm. Patients will have an INR/PT

performed at the time of study enrolled (if not within the past 3 months) to confirm no hepatic impairment.

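### The hepatic exclusion sets a Child-Turcotte-Pugh cut-off of 2, which on the standard scale every patient meets, so as written it cannot identify hepatic impairment

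*Combined protocol and SAP*

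**What the plan says.** Section 6.b, Exclusion Criteria, contains one hepatic criterion: "Hepatic impairment as defined by patients with a Child-Turcotte-Pugh score" of 2 or more, "based on a CMP/INR/PT performed within 3 months of study enrollment". The text calls the quantity a score. It does not list the items, the points per item, the range or the classes, and the reference list has no source for the instrument.

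Three other places depend on this criterion:

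- Section 9, Laboratory Monitoring, requires an INR/PT "performed at the time of study enrolled (if not within the past 3 months) to confirm no hepatic impairment".
- Section 6.c gives the target: "This is a pilot study which aims to enroll 30 patients locally, 15 per arm".
- Section 6.k lists, among the circumstances in which a provider may withdraw a subject, "Failure to meet inclusion/exclusion criteria (labs, A1c, ECG parameters").

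**The concern.** An exclusion threshold has to lie inside the range of the scale, so that some patients fall on each side of it. A cut-off of 2 appears to lie below the lowest value this score can take. If so, a patient with an entirely normal liver meets the definition of hepatic impairment, and the criterion carries no information.

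Two things are at stake. The first is whether eligibility can be reproduced: under sections 6.a and 6.f the provider who sees the patient does the screening, and a provider who cannot apply the rule literally has to interpret it. The second is the safety purpose of the criterion. It is the only hepatic exclusion, and section 7 says that this combination of supplements has not been studied together in humans and that its risks are unknown.

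The stated data source raises a further problem. The protocol bases the score on blood tests alone, although two components of the instrument are clinical findings.

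**Working it through.** The plan gives no derivation of the cut-off, so there is no figure to reproduce. The check is to enumerate the possible totals and count how many reach 2.

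**Inputs from the documents.** The cut-off is a score of at least 2, and the data source is CMP and INR/PT (both section 6.b).

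**Input assumed.** Standard scoring of the named instrument: five items (bilirubin, albumin, INR/PT, ascites, encephalopathy), each scored 1, 2 or 3. The documents do not give this.

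**Literal reading, full score.** Minimum = 5 × 1 = 5; maximum = 5 × 3 = 15. Number of item combinations = 3^5 = 243. All 243 reach 2.

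**Literal reading, laboratory items only.** The CMP and INR/PT supply bilirubin, albumin and INR/PT. Minimum = 3 × 1 = 3; maximum = 3 × 3 = 9. Combinations = 3^3 = 27. All 27 reach 2.

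**Range over readings that the text does not state.**

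| Reading | Range | Outcomes meeting the cut-off of 2 | All-normal patient excluded? |
|---|---|---|---|
| Five items, 1–3 (standard) | 5–15 | 243 of 243 | Yes |
| Three laboratory items, 1–3 | 3–9 | 27 of 27 | Yes |
| Five items re-scored 0–2 | 0–10 | 237 of 243 | No |
| Three laboratory items re-scored 0–2 | 0–6 | 23 of 27 | No |
| Classes A/B/C coded 1/2/3 | 1–3 | 2 of 3 classes | No |

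The counts are of possible score patterns, not of patients. In the 0–2 rows, the patterns that pass are those with no abnormal item or a single item one point up: 1 + 5 = 6 = 243 − 237 for five items, and 1 + 3 = 4 = 27 − 23 for three.

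**Comparison with the other sections.** Section 9 has the INR/PT drawn "to confirm no hepatic impairment", which presupposes that a patient with normal results passes. Section 6.c plans 30 enrolled patients. Under both literal readings nobody passes, so section 6.b conflicts with both. Read literally together with section 6.k, every enrolled patient would also have a ground for withdrawal.

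**Data source.** Of the five items, 5 − 3 = 2 (ascites and encephalopathy) are not laboratory values. The named source therefore cannot produce the full score, whatever the cut-off.

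**The case against.** The strongest reply is that the decisive input, a minimum of 5, is not in the documents, and that a sensible reader would see what was meant. If 2 denotes the second class, or two points above the minimum, a patient with normal results passes and the criterion works. The plan to enrol 30 shows that nobody intends to exclude everyone.

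Part of this stands. The scale minimum is an assumption and the conclusion depends on it. The class and 0–2 readings may also lie close together: if class A covers totals of 5 and 6 (again an assumption), the class reading and the five-item 0–2 reading exclude the same patients. But the text says score, not class, and mentions no re-scoring. A laboratory-only version differs from both for any patient with a clinical finding, and it is the version closest to the stated data source. A provider who excludes for any abnormal test would be applying yet another rule.

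It can also be said that other safeguards exist. Section 6.f has missing baseline tests performed to check for normal values before study activities continue. Section 9 adds a closing CMP in the treatment arm, discontinuation of the supplement by adverse-event grade, and committee review after every 5 patients. These are real, but none of them defines hepatic eligibility.

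A reader might infer three stronger points that the documents do not support:

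- That the trial cannot enrol anyone. This follows only from literal application, which sections 6.c and 9 show is not intended.
- That the faulty cut-off removes the screen for the raised ALT and AST listed in section 7. Neither enzyme is an item of the score, so correcting the cut-off would not screen for them.
- That the treatment comparison is biased. The criterion is applied at Visit 0 before randomisation, so ambiguity falls on both arms alike.

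**Conclusion.** The hepatic exclusion is wrong as written. Assuming 1 to 3 points per item, the cut-off of 2 is met by every possible score, whether the full five items (minimum 5) or the three laboratory items (minimum 3) are used, so it cannot identify hepatic impairment. It would discriminate only under a re-scoring or class coding that the documents do not state. It is inconsistent with the enrolment target in section 6.c and with the purpose of the INR/PT in section 9. The stated data source also omits two of the five items.

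The likely practical consequence is an undefined threshold, applied inconsistently, on the only hepatic exclusion. How often providers would differ cannot be estimated from the documents. The primary outcome and its analysis are unaffected, and no sample size, power or alpha figure changes.

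**What to change.** The sponsor should reconcile sections 6.b, 6.c and 9:

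1. In section 6.b, replace the cut-off of 2 with the threshold that was intended, expressed on the scale actually used: total score, class, or a named laboratory-only version.
2. State which items are scored and the source of each.
3. Use the same definition in section 9, Laboratory Monitoring.

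No particular cut-off is proposed here; only the sponsor can say what was meant.

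The cost is a short amendment that uses laboratory tests already required. If the full score is kept, there is one small addition. The Visit 0 list in section 6.f does not include a general history or physical examination (interval ones appear at Visits 1 to 3), so a brief recorded assessment of the two clinical items would have to be added there. No extra visit is needed.
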